5.9 Suggested Guidelines for Management of Infusion-related Reactions

Criteria for categorizing IRRs are provided in [Appendix 3](#).

- In the event of an IRR, the infusion of study drug may be stopped and the patient closely monitored until resolution of the reaction. Drugs that may be used to facilitate resolution and permit resumption of study drug administration include, but are not limited to: paracetamol/acetaminophen (or equivalent), additional histamine H1/H2 receptor antagonists (eg, ranitidine), NSAIDs, adrenaline, supplemental oxygen, IV fluids, and/or corticosteroids.

- Following resolution of a mild or moderate IRR that required interruption of the study drug infusion, resumption of administration may occur at the Investigator's discretion at a slower infusion rate (but not to exceed 3 hours) for that dose and for all subsequent doses of study drug. If the infusion is delayed, the administration of the infusion should be completed no more than 6 hours from the initial start of the infusion.
- Study drug administration will not be resumed for any patient following a severe IRR until the case is discussed with the Medical Monitor.
- If after consultation with the medical monitor it is agreed that an individual patient's steroid premedication will be increased then the following steps are **recommended**:
 - 1) If the IRR occurred while the patient received 10 mg intravenous dexamethasone or equivalent at least 60 minutes before the infusion and did not resolve with slowing of the infusion rate, then the patient should be increased by multiples of 5 mg intravenous dexamethasone or equivalent at least 60 minutes before the infusion and/or 5 mg oral dexamethasone or equivalent the night before the intravenous infusion.
 - 2) Increased dose of premedication steroids should NOT exceed the combination of 20 mg intravenous dexamethasone or equivalent on the day of infusion and 8 mg oral dexamethasone or equivalent taken the night before the infusion.
 - 3) If the IRR occurred while the patient received less than 10 mg intravenous dexamethasone or equivalent, then the patient should return to the prior dose of intravenous dexamethasone or equivalent that did not result in an IRR.

The patient's infusion site should be assessed for signs of any localized reaction during the infusion and for 30 minutes after the end of the infusion. The patient will remain at the study site for 1 hour following completion of dosing for observation and completion of assessments. Patients will be instructed to call the Investigator if they experience symptoms such as fever, chills, myalgia, or nausea/vomiting after discharge from the site.

6 STUDY VISITS

The duration of a patient's participation in this study is approximately 21 months (inclusive of a 42-day screening period and up to a 56-day post last dose study visit).

Screening evaluations are to be performed within 42 days before receiving the first dose of study drug, as indicated in [Table 1-1](#). Patients determined to be eligible based on Screening assessments will receive blinded study drug IV infusion of either patisiran (ALN-TTR02) or placebo once every 21 days. Patients will remain at the study site for 1 hour following completion of dosing for observation and completion of assessments.

In order to decrease the variability in the efficacy assessment testing, there will be a limited number of sites within any one territory that conduct efficacy assessments at Screening/Baseline, Baseline, 9-month, and 18-month visits (referred to as "Central Assessment Sites [CAS]"); these sites can also screen, dose, and manage patients. There will also be sites that screen, dose, and manage the patients ("Patient Care Sites [PCS]"), while sending the patients to the nearest CAS for their Screening/Baseline, Baseline, 9- and 18-month efficacy assessments.

Prior to starting the study and screening patients in the protocol, the CAS and PCS will create a delegation of responsibilities document that clearly details which site is responsible for which tests and safety parameters to ensure adherence to the protocol. This document will become part of the study site specific documentation.

All patients who discontinue from the study early will return to the study site for their Early Withdrawal assessments.

6.1 Screening, Screening/Baseline, and Baseline Visits (Days –42 to Day 0)

Screening evaluations will be conducted over 3 or more visits (Screening, Screening/Baseline, and Baseline). All screening visits must occur within 42 days of the first dose of study drug (Day 0). [Table 1-1](#) provides an overview of the schedule of events required at each screening visit.

Prior to screening activities, the patient will sign and date an informed consent form (ICF) and receive a copy of the signed ICF. No study procedures should be performed prior to informed consent being obtained. The Investigator or another person authorized by the Investigator will also sign and date the informed consent prior to giving a copy to the patient. The ICF will be filed in the patient's medical record.

In conjunction with the decision of the Medical Monitor(s), patients may be allowed to rescreen after a minimum of 5 days have elapsed from their last screening assessment.

6.1.1 Screening

The following activities must be performed during the Screening visit as part of the initial review of patient eligibility:

- Assess study eligibility using the inclusion and exclusion criteria;
- Obtain medical history information, including inquiry into HIV status;
- Obtain demographic information;

- Determine Karnofsky Performance Status (see [Appendix 1](#));
- Determine New York Heart Association classification of heart failure (see [Appendix 2](#));
- Collect and review documentation for TTR genotype;
- Perform a physical examination;
- Measure weight;
- Measure height;
- Measure vital signs;
- Collect blood samples for clinical laboratory tests, including:
 - Paraprotein (assessed by immunofixation electrophoresis [IFE]);
 - Vitamin B₁₂;
 - Serology;
 - Hematology;
 - Serum chemistries;
 - Coagulation studies;
 - Thyroid function tests.
- Collect urine sample for urinalysis;
- Perform a pregnancy test (for females of child-bearing potential only);
- Obtain information on concomitant medications;
- Perform NIS and NCS. Note: The documented results of previously performed NIS and NCS may be used to qualify a patient for this study if these tests were performed within 60 days prior to the date of informed consent. These studies may be completed as per local protocol.

6.1.2 Screening/Baseline Visit

Patients who meet all of the Screening criteria (including NIS and NCS assessments) will complete the screening process during 2 subsequent visits (which will be conducted at CAS for patients screened at PCS): a Screening/Baseline visit and a Baseline visit.

The Screening/Baseline visit must be performed within 21 days prior to the first dose of study drug (Day 0).

The following assessments must be performed during the Screening/Baseline visit:

- Perform the following efficacy assessments:
 - mNIS+7*;
 - NIS+7*;

*Note: Components that are shared between the mNIS+7 and NIS+7 (including NIS and NCS) will be performed only once.

- PND score;
- Collect blood sample for long-term frozen storage of serum to permit testing of additional proteins related to FAP;
- Measure vital signs;
- Measure weight;
- Obtain information on concomitant medications;
- Obtain an interval medical history;
- Confirm that NIS, PND, and NCS results meet study eligibility requirements. Inclusion Criteria 3 (i.e., NIS of 5 to 130 [inclusive] and PND score of $\leq 3b$) and 4 (i.e., NCS sum of the sural SNAP, tibial CMAP, ulnar SNAP, ulnar CMAP, and peroneal CMAP of ≥ 2 points).

Note: The following assessments may be performed at a single time point during either the Screening/Baseline visit or as noted below, at the discretion of the investigator.

At the Screening/Baseline or Baseline visit:

- Perform a 12-lead ECG;
- Complete the Norfolk QOL-DN, and COMPASS-31 questionnaires;
- Complete the C-SSRS questionnaire;

At any time after the patient is deemed eligible for participation in the study, but before the first administration of study drug:

- Perform a timed 10-meter walk test.

At any time after the patient is deemed eligible for participation in the study through the Day 0 visit:

- Perform a grip strength test;
- Perform an echocardiogram;
- Complete the EQ-5D and R-ODS questionnaires;

At any time after the patient is deemed eligible for participation in the study through the Day 21 visit:

- Perform an ophthalmology exam;
- Complete the pharmacoeconomics questionnaire.

6.1.3 Baseline Visit

The Baseline visit will occur at least 24 hours (approximately), but no greater than 7 days, from the Screening/Baseline visit. The following activities should be performed during the Baseline visit:

- Perform a 12-lead ECG (if not completed at the Screening/Baseline visit);
- Measure vital signs;

- Measure weight;
- Collect blood sample for serum TTR protein, RBP, and vitamin A. Additionally, aliquots of serum samples will be taken for long-term frozen storage, to permit testing of additional proteins related to FAP;
- Obtain information on concomitant medications;
- Perform the following efficacy assessments:
 - mNIS+7*;
 - NIS+7*;
 - *Note: Components that are shared between the mNIS+7 and NIS+7 (including NIS and NCS) will be performed only once.
 - PND score (see [Appendix 5](#));
 - FAP stage (see [Appendix 6](#));
 - If the patient has provided separate informed consent for the skin biopsies, obtain 2 sets of tandem 3-mm skin punch biopsies (4 biopsies total; 1 set from the distal lower leg, when a patient's clinical status allows, and 1 set from the distal thigh). Skin biopsies will be performed at a CAS;
 - mBMI (Note: The site will only measure the patient's weight. Using this weight, mBMI will be calculated programmatically in the clinical database; the site will not perform the calculation.);
 - Collect blood samples for NT-proBNP and troponin I;
 - Norfolk QOL-DN (if not completed at the Screening/Baseline visit);
 - COMPASS-31 (if not completed at the Screening/Baseline visit).
- Complete the C-SSRS questionnaire (if not completed at the Screening/Baseline visit);
- Obtain an interval medical history.

The following activities may also be completed at the Baseline visit if not completed at the Screening/Baseline visit, as described in [Section 6.1.2](#):

- Timed 10-meter walk test;
- Grip strength test;
- Echocardiogram;
- EQ-5D and R-ODS questionnaires;
- Ophthalmology examination at a CAS;
- Pharmacoeconomics questionnaire.

6.2 Treatment Visits

Patients who are determined to be eligible for the study will be enrolled on Day 0.

On all study visit days, patients should take their vitamin A supplement after completing the blood draws.

Prior to dosing, all patients will receive premedications in order to reduce the risk of experiencing an IRR as described in [Section 5.3.1](#).

6.2.1 Day 0

6.2.1.1 Pre-dose on Day 0

On Day 0, patients will undergo the following procedures prior to study drug administration:

- Measure weight;
- Measure vital signs;
- Timed 10-meter walk test (if not completed at the Screening/Baseline or Baseline visits);
- Collect blood samples for clinical laboratory tests, including:
 - Serum chemistries;
 - Anti-drug antibody testing.
- Collect blood sample for serum TTR protein, RBP, and vitamin A. Additionally, aliquots of serum samples will be taken for long-term frozen storage, to permit testing of additional proteins related to FAP;
- Collect blood sample for plasma PK assessment within 1 hour of planned study drug dosing start;
- Collect urine sample for PK assessment within 1 hour of planned study drug dosing start;
- Obtain information on concomitant medications;
- Randomize the patient (See [Section 4.4.1](#));
- Administer premedications at least 60-minutes prior to the start of administration of study drug (see [Section 5.3.1](#));
- Document any AEs.

The following activities are to be completed on Day 0 pre- or post-dosing if not completed at the Screening/Baseline or Baseline visits, as described in [Section 6.1.2](#):

- Grip strength test;
- Echocardiogram;
- EQ-5D and R-ODS questionnaires.

6.2.1.2 Administration of Study Drug on Day 0

As described in [Section 5.3.2](#), after completion of all pre-dose evaluations and procedures, study drug will be administered by a controlled infusion device as a 70-minute IV infusion (approximately 1 mL/minute for the first 15 minutes followed by approximately 3 mL/minute for the remainder of the infusion) or at a more prolonged infusion rate (up to 3 hours) if required due to prior IRR. The patient's infusion site should be assessed for signs of any localized reaction during the infusion and for 30 minutes after the end of the infusion.

The infusion time may be extended up to 3 hours in the event of a mild or moderate IRR. Study drug administration will not be resumed for any patient following a severe infusion reaction until the case is discussed with the Medical Monitor.

Suggested guidelines for management of IRRs are provided in [Section 5.9](#).

6.2.1.3 Post-dose on Day 0

The patient's infusion site should be assessed for signs of any localized reaction during the infusion and for 30 minutes after the end of the infusion. The patient will remain at the study site for 1 hour following completion of dosing for observation and completion of assessments:

- Measure vital signs;
- Collect a PK sample at the end of infusion (+5 minutes);
- Obtain information on concomitant medications;
- Document any AEs.

The following activities may also be completed on Day 0 if not completed at the Screening/Baseline or Baseline visits, as described in [Section 6.1.2](#):

- Ophthalmology examination at a CAS;
- Pharmacoeconomics questionnaire.

6.2.2 Routine Study Visits

The procedures described below are to be performed for all routine study visits (from Day 21 through Day 546), with the exception of the 9-month and 18-month efficacy assessments (occurring on Days 253-272 and Days 553-560, respectively). All visits have a window of "±3 days" except for the Day 273 visit which has a window of "+3 days" to allow adequate time for the assessment of the patient's 9-month mNIS+7 and FAP stage testing, which will determine if the patient met the criteria for Rapid Disease Progression.

Patients will undergo the following procedures before study drug dosing:

- At all dosing visits, administer premedications at least 60 minutes prior to the start of administration of study drug (see [Section 5.3.1](#));
- At all dosing visits, measure weight;
- At all dosing visits, measure vital signs;

- On Days 252 and 546, perform a physical examination;
- On Days 126 and 399, perform a 12-lead ECG;
- On Days 21, 126, 252, 273, 399, and 546, collect blood sample for serum TTR protein, RBP, and vitamin A. Additionally, aliquots of serum samples will be taken for long-term frozen storage, to permit testing of additional proteins related to FAP;
- On Days 84, 189, 357, 462, and 546, collect blood samples for serum chemistry tests;
- On Day 546, collect blood sample for INR;
- On Days 21, 126, 252, 399, and 546, collect a blood sample for anti-drug antibody assessment;
- On Days 252 and 546, collect blood samples for clinical laboratory tests, including:
 - Hematology;
 - Thyroid function tests.
- On Days 252 and 546, collect urine sample for urinalysis;
- On Days 21, 126, 252, 399, and 546, collect a plasma PK sample pre-dose (within 1 hour of planned study drug dosing);
- On Days 21, 126, 252, 399, and 546, collect a urine PK sample pre-dose (within 1 hour of planned dosing start);
- Perform ophthalmology examinations on Day 21 (if baseline examination was not completed prior to the Day 21 visit), once between Days 231(\pm 3) and 272 at a CAS, and once between Days 546(\pm 3) and 560 at a CAS;
- Complete the pharmacoeconomics questionnaire on Day 21, if not completed prior to the Day 21 visit;
- At all dosing visits, obtain information on concomitant medications;
- At all dosing visits, document any AEs.

Following the completion of all required pre-dose activities and assessments, administer the study drug at all dosing visits, as described in [Section 6.2.1.2](#).

Following dosing, collect plasma PK samples as follows:

- On Days 126 and 399, collect a plasma PK sample at the end of the infusion (+5 minutes);
- On Days 21, 252, and 546, collect a plasma PK sample 30 minutes after the end of the infusion (+15 minutes).

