1.6 Risk-Benefit Assessment

Patisiran is a novel investigational agent intended for the treatment of FAP, a serious and life-threatening orphan disease with limited treatment options. The therapeutic hypothesis that systemic amyloidoses can be managed by reducing circulating levels of amyloidogenic protein has been established in other acquired and hereditary amyloidoses. The experience from these systemic amyloidotic disorders, as well as the liver transplant data in FAP, suggest that lowering of the circulating amyloidogenic protein could impact the clinical course of the disease. Based on nonclinical and clinical data that showed suppression in

levels of WT and mutant TTR upon administration of 0.3 mg/kg patisiran once every 21 days, it is possible that long term treatment with patisiran may have a clinical benefit in FAP patients with mild to moderate polyneuropathy and that further study is warranted.

In completed and ongoing clinical studies (ALN-TTR02-001, ALN-TTR02-002 and ALN-TTR02-003), single and multiple doses of patisiran have been generally well tolerated. Potential risks of patisiran include the following:

- **Infusion-Related Reactions**

Infusion-related reactions (IRRs) can occur with systemic administration of certain biological agents such as liposomes or monoclonal antibodies. In order to reduce the potential for an IRR with patisiran, all patients in this study will be premedicated prior to dosing with patisiran or placebo. The step-wise infusion regimen over approximately 70 minutes (starting with a slower infusion rate of approximately 1 mL/minute for the first 15 minutes before increasing to 3 mL/minute for the remainder of the infusion), may further reduce the risk of an IRR.

- **Liver function test abnormalities**

In preclinical studies, patisiran-related increased serum liver markers and histopathology in the liver were observed at dosages > 0.1 mg/kg in rats and > 1.0 mg/kg in monkeys. In general, all of the findings were not observed or were observed at lower severity at the end of the 60-90 day dose free period, indicating that the toxicities were reversible. In clinical studies to date, there have been no clinically significant changes in liver function tests in either the single-dose or multiple-dose studies. Patients in the study are monitored for liver function via serial laboratory assessments.

- **Vitamin A Lowering**

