5.3.2 Study Drug Administration

Patients who are randomized into the active treatment group will receive 0.3 mg/kg patisiran once every 21 days (\pm 3 days). Patients who are randomized into the control group will receive placebo (normal saline 0.9%) once every 21 days (\pm 3 days).

The body weight that was obtained during the previous visit must be used to calculate the dose of study drug. In the event that the body weight obtained on the previous dosing day is not available, the body weight obtained pre-dose on the dosing day can be used for the dose calculation. Patients who weigh 105 kg or more will receive patisiran dosing based on an assumption of a body weight of 104 kg.

Study drug (either patisiran or placebo) will be administered under the supervision of the unblinded site personnel, as a 70-minute IV infusion (approximately 1 mL/minute for the first 15 minutes followed by approximately 3 mL/minute for the remainder of the infusion). The study drug will be administered via a controlled infusion device with an extension set containing a 1.2 micron filter supplied by Alnylam or designee. Infusion products must not contain polyvinyl chloride, di(2-ethylhexyl)phthalate (PVC, DEHP). As described in [Section 4.4.3](#), the tubing and the lines will be covered so that it will not be possible to detect a difference in active versus placebo drug.

- If the patient experiences an IRR the infusion time may be extended up to 3 hours in the event of a mild or moderate IRR.
 - 1) If the patient experiences a mild or moderate IRR that resolves by slowing the infusion rate then no further premedication changes are recommended.
 - 2) If the patient experiences a severe IRR, then study drug administration will not be resumed until the case is discussed with the medical monitor (see [Section 5.9](#)).
- If the infusion time for a patient was extended due to an IRR, that modified infusion duration should be continued throughout the duration of the study for that particular patient. Returning the patient's infusion duration to 70 minutes will require a discussion with the medical monitor.
- For the first 3 infusions of study drug on this study, the patient's infusion site should be assessed for signs of any localized reaction during the infusion and for 30 minutes after the end of the infusion, and the patient will remain at the clinical site for 1 hour following completion of dosing.

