6.2.3 Efficacy Assessment Visits (9 Months and 18 Months)

Efficacy assessment will be performed on all patients at approximately 9 and 18 months (Days 253-272 and 553-560, respectively). Patients will not receive any study drug on these days.

As described in [Section 4.6](#), in consultation with the Investigator on Day 273 (+3 days), patients who meet the criteria for Rapid Disease Progression based on the 9-month efficacy assessments may continue study drug dosing or discontinue study drug dosing. Patients who discontinue study drug dosing may receive additional therapy for FAP, as per the local standard of care. These patients will remain on the study and follow the modified schedule of assessments shown in [Table 1-3](#) and described in [Section 6.4](#). Blinding will be maintained throughout.

The 9- and 18-month efficacy assessment visits will take place over 2 days.

- Perform the following efficacy assessments:

- mNIS+7*;
- NIS+7*;
- Timed 10-meter walk test*;
- Grip strength test*;

*Note: For the mNIS+7, NIS+7, timed 10-meter walk test, and grip strength test, an independent assessment will be performed on each day. Each site will make every effort to have these assessments performed by the same Investigator. Assessments are to be performed at least 24 hours (approximately) apart from each other but no greater than 7 days apart. For the mNIS+7 and NIS+7, components that are shared (including NIS and NCS) will be performed only once on each assessment day.

- PND score (see [Appendix 5](#));
 - FAP stage (see [Appendix 6](#));
 - If the patient has provided separate informed consent for the skin biopsies, obtain 2 sets of tandem 3-mm skin punch biopsies (4 biopsies total); 1 set from the distal lower leg when a patient's clinical status allows, and 1 set from the distal thigh. Skin biopsies will be performed at a CAS;
 - mBMI (Note: The site will only measure the patient's weight. Using this weight, mBMI will be calculated programmatically in the clinical database; the site will not perform the calculation.);
 - Echocardiogram;
 - Collect blood samples for NT-proBNP and troponin I;
 - Norfolk QOL-DN;
 - EQ-5D;
 - R-ODS;
 - COMPASS-31.
- Measure weight on both efficacy assessment days;
 - Measure vital signs on both efficacy assessment days;

- Complete the C-SSRS questionnaire;
- Complete the pharmacoeconomics questionnaire;
- Perform a 12-lead ECG;
- Collect blood samples for:
 - TTR protein, RBP, and vitamin A;

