7.5.5 Clinical Laboratory Tests

Blood samples for clinical laboratory testing will be collected prior to study drug dosing at the time points listed in [Table 1-1](#), [Table 1-2](#), and [Table 1-3](#). Samples will be sent to a central laboratory for analysis. Details on sample collection, processing, and shipping will be provided in a Laboratory Manual.

In the event of an unexplained clinically relevant abnormal laboratory test occurring after study drug administration, the test should be repeated and followed up at the discretion of the Investigator until it has returned to the normal range or stabilized, and/or a diagnosis is made to adequately explain the abnormality.

The following clinical laboratory parameters are to be determined:

Hematology	
• Hematocrit	• Neutrophils, absolute and %
• Hemoglobin	• Lymphocytes, absolute and %
• Red blood cell (RBC) count	• Monocytes, absolute and %
• White blood cell (WBC) count	• Eosinophils, absolute and %
• Mean corpuscular volume	• Basophils, absolute and %
• Mean corpuscular hemoglobin	• Platelet count
• Mean corpuscular hemoglobin concentration	
Serum Chemistries	
• Aspartate transaminase (AST)	• Alkaline phosphatase
• Alanine transaminase (ALT)	• Bilirubin (total and direct)
• Sodium	• Glucose
• Potassium	• Phosphate
• Blood urea nitrogen (BUN)	• Albumin
• Creatinine	• Calcium

Coagulation Studies	

 Prothrombin time (PT) Activated partial thromboplastin time (aPTT) 	
 International Normalized Ratio (INR)
Thyroid Function Tests	

 Thyroid stimulating hormone (TSH) Thyroxine (Free T4) 	
 Triiodothyronine (Free T3)
Anti-drug Antibodies	

 Anti-PEG antibodies 	
Urinalysis	

 Visual inspection for color and appearance pH Specific gravity Ketones Protein Glucose 	
 Leukocytes Bilirubin Nitrite Urobilinogen Microscopic inspection of sediment
Serology	

 Hepatitis B surface antibody (HbsAb) Hepatitis B surface antigen (HbsAg) 	
 Anti-hepatitis C virus antibody (anti-HCVAb)
Cardiac Biomarkers	

 N-terminal prohormone of B-type natriuretic peptide (NT-proBNP) Troponin I 	
Other	

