1.2.7. Efficacy, Pharmacokinetic, Pharmacodynamic, and Safety Parameters

1.2.7.1. Efficacy Parameters

Efficacy parameters will include the following. All evaluations will be conducted at baseline and at 9 and 18 months (except for mBMI as described below).

Primary Endpoint

- Neurologic impairment will be assessed using the mNIS+7 composite score (range: 0 to 304 points). The mNIS+7 include the modified NIS (weakness and reflexes), Σ 5 NCS, QST, as well as autonomic assessment through postural blood pressure. Two assessments will be performed at each visit; each component contributing to the composite score is the average of the 2 assessments. A scoring algorithm, including methods for handling missing components of the mNIS+7, is included in Appendix 7.2.1.

Secondary Endpoints

- Patient reported QOL will be evaluated using the Norfolk QOL-DN total score (range: -4 to 136 points). A scoring algorithm for this instrument is included in Appendix 7.2.2.
- Motor strength will be evaluated using NIS-W, calculated as the average of the 2 assessments performed at each visit (range: 0 to 192 points).

- Level of disability will be assessed using the Rasch-built Overall Disability Scale (R-ODS; range: 0 to 48). A scoring algorithm for the R-ODS is included in Appendix [7.2.4](#).
- Functional status will additionally be assessed by 10-meter walk gait speed.
- Nutritional status will be assessed using mBMI, calculated by multiplying the BMI (kg/m²) by serum albumin level (g/L). mBMI will be assessed at baseline, Day 84, Day 189, Day 357, Day 462 and Day 546.
- Autonomic symptoms will be assessed using the COMPASS-31 total score (range: 0 to 100 points). A scoring algorithm for the COMPASS-31 total score and domain scores is included in Appendix [7.2.5](#).

Exploratory Endpoints

Exploratory endpoints are detailed in Section [1.1.2.3](#).

In addition, the evaluation of dermal amyloid content (% Congo Red staining) using same skin punch biopsy specimens analyzed for nerve fiber density (SGNFD and IENFD) will also be assessed as an exploratory endpoint.

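### On the standard schedule, serum chemistry is not drawn between Day 189 and Day 357, which leaves 168 days between scheduled liver tests and no albumin for the protocol's 9-month mBMI

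*Protocol*

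**What the plan says.** **Chemistry days.** Protocol 6.2.2 lists them: "On Days 84, 189, 357, 462, and 546, collect blood samples for serum chemistry tests". Section 6.2.1.1 adds a pre-dose sample on Day 0. Section 7.5.5 puts AST, ALT, bilirubin, creatinine and albumin in the serum chemistry panel and in no other.

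**The Month 9 safety draw.** Section 6.2.2 also states: "On Days 252 and 546, collect blood samples for clinical laboratory tests, including", and the list that follows is hematology and thyroid tests. Day 546 appears in both lists. Day 252 appears only in the second. Blood is also taken on Day 252 for TTR, anti-drug antibody and PK.

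**Liver risk.** Protocol 1.6 names liver function abnormality as a potential risk and gives the safeguard: "Patients in the study are monitored for liver function via serial laboratory assessments". It states no interval.

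**mBMI.** Protocol 7.2.5 defines it as BMI times albumin. Section 6.2.3 and Table 1-1 schedule it at the 9-month visit: "mBMI (Note: The site will only measure the patient's weight". No albumin sample is listed there. The SAP (1.2.7.1) has different days: "mBMI will be assessed at baseline, Day 84, Day 189, Day 357, Day 462 and Day 546". SAP 4.3.2 takes Day 546 as Month 18.

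**Patients who stop treatment and return.** Protocol 6.3.2 lists mBMI at Months 9 and/or 18. Blood is drawn for TTR, RBP, vitamin A and PK, but not for chemistry.

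**The concern.** Two things depend on the same missing sample.

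The first is safety data. SAP 4.6.3 classifies patients by their ALT, AST and bilirubin values after baseline, including concurrent elevations, and tabulates worst post-baseline eGFR category. These summaries show only what was sampled. A rise that begins after Day 189 and settles before Day 357 would not meet any scheduled test. That window is well over half as long again as any other on-treatment interval, although blood is taken inside it at visits that already exist.

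The second is a secondary endpoint measure. The protocol schedules a 9-month mBMI that its own sampling plan cannot support with an albumin value from near that visit. The SAP resolves this by leaving Month 9 out for mBMI alone. SAP 1.1.2 undertakes to outline differences from the protocol, yet SAP section 5 does not mention this one. For the returning patients in Protocol 6.3.2 the fault also reaches Month 18, which is the time point of the secondary objective.

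**Working it through.** The documents state no interval or dose count to reproduce, so this is date arithmetic on the dosing grid.

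**Inputs.**
- Dosing: "Patients who are randomized into the active treatment group will receive 0.3 mg/kg patisiran once every 21 days" (Protocol 5.3.2). Day 0 to Day 546 in 21-day steps gives 546/21 + 1 = 27 doses and ends at 546/7 = week 78, which matches the protocol.
- Sampling order: "Blood samples for clinical laboratory testing will be collected prior to study drug dosing at the time points listed in" the schedule tables (Protocol 7.5.5). The dose on a sampling day therefore follows that day's sample.
- Chemistry days: 0, 84, 189, 357, 462, 546. The text of 6.2.1.1 and 6.2.2 was used because the table rows are partly displaced in extraction. The post-baseline days agree with the SAP's mBMI days.

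**Intervals.** Interval = later day minus earlier day. Doses = interval/21, counting the dose on the earlier sampling day.

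| From | To | Days | Doses |
|---|---|---|---|
| 0 | 84 | 84 | 4 |
| 84 | 189 | 105 | 5 |
| 189 | 357 | 168 | 8 |
| 357 | 462 | 105 | 5 |
| 462 | 546 | 84 | 4 |

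The eight doses are Days 189, 210, 231, 252, 273, 294, 315 and 336. Leaving out Day 189 gives seven. With a ±3-day window at each end, the interval is 168 ± 6, or 162-174 days.

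**Exception.** Patients who stop drug for rapid progression have chemistry on modified Day 294 (Protocol 6.4.2). Their interval is 294 − 189 = 105 days, with four doses (Days 189, 210, 231, 252).

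**Albumin and the efficacy visits.** The 9-month window is Days 253-272.
- From Day 189: 253 − 189 = 64 to 272 − 189 = 83 days before the visit.
- To Day 357: 357 − 272 = 85 to 357 − 253 = 104 days after it.
- At Month 18 (Days 553-560), from Day 546: 553 − 546 = 7 to 560 − 546 = 14 days before.

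**With chemistry added on Day 252.**
- 252 − 189 = 63 days (3 doses) and 357 − 252 = 105 days (5 doses). The longest interval falls from 168 to 105 days, equal to the longest elsewhere.
- Albumin would precede the 9-month visit by 253 − 252 = 1 to 272 − 252 = 20 days.

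**The case against.** **No rule is broken.** This stands. Protocol 1.6 promises serial tests without an interval, and it reports no clinically significant liver test changes in clinical studies to date. Sparse safety laboratories are general in this protocol: hematology and thyroid tests on treatment fall only on Days 252 and 546, which are 546 − 252 = 294 days apart.

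**A reader might infer that a Month 9 sample was dropped by mistake**, because a Day 273 sample would split the 168 days into 84 and 84. The documents do not support that. Section 6.2.2 and the SAP's mBMI days agree with each other, and neither shows a lost entry.

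**A reader might infer that a transient rise in the gap could never be seen, or that no patient could have a 9-month mBMI.** Both go too far. Unscheduled visits are allowed (Protocol 6.5), and Early Withdrawal visits include chemistry (6.3.1). SAP 3.9 lets unscheduled results enter the shift summaries and groups a discontinuation visit with Month 9 if it falls within three months of a missed visit. Rapid progressors who stop drug are sampled on Day 294. Section 7.2.5 also does not say that albumin must be taken on the same day as weight. A shorter interval could miss a transient rise too.

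**The SAP already handles mBMI.** This largely stands for the standard schedule. The objective is change at 18 months, and SAP 4.3.2 estimates it from a repeated-measures model on five post-baseline days that does not need Month 9. It does not explain the undeclared difference from the protocol, and it does not help the patients in 6.3.2.

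**It may be too late.** SAP 5.4 says that enrollment was complete when that amendment was written, so some or all patients may be past Day 252.

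**Conclusion.** The point holds as a design weakness in safety data collection together with an inconsistency between protocol and SAP. On the standard schedule the interval across Month 9 is 168 days and 8 doses (or 7), against 84-105 days and 4-5 doses elsewhere. The 9-month mBMI has no albumin within 64 days before or 85 days after the visit. For patients who stopped treatment and return under Protocol 6.3.2, mBMI at Months 9 and 18 has no albumin scheduled with it.

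This rests on nominal visit days and on scheduled samples only. It does not show a breach of a stated monitoring rule or a missed liver signal. Nor does it show bias or loss of power in the Month 18 mBMI test on the standard schedule, since no planned analysis uses a Month 9 mBMI. It is worth correcting because the remedy is small and the blood draw already exists.

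**What to change.** 1. Add serum chemistry to the existing Day 252 pre-dose draw in Table 1-1 and Protocol 6.2.2, as is done on Day 546.
2. Add albumin to the blood draw already taken at the Protocol 6.3.2 visits, and state in the SAP that the 18-month value counts as Month 18 for these patients, who have no Day 546 dosing visit.
3. Reconcile the protocol's 9-month mBMI entry with SAP 1.2.7.1 and 4.3.2. Either add Day 252 as an mBMI time point or list the omission of Month 9 in SAP section 5.
4. For patients already past Day 252, make the reconciliation in step 3 by declaring the omission, and report the 168-day sampling gap beside the liver tables of SAP 4.6.3.

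The cost is one extra tube and a laboratory fee per sample, with short edits to the schedule and the SAP. No new visit or staff is needed. One drawback is that Day 252 albumin may precede the Month 9 weight by up to 20 days. Weight is also measured on Day 252 and can be used instead, so that both parts of mBMI come from the same day.
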